3.5 Supportive Care

All supportive measures consistent with optimal patient care will be given throughout the study.

3.6 Duration of Agent-specific treatment

In the absence of treatment delays due to adverse event(s), treatment may continue until one of the following criteria applies:

- Extraordinary Medical Circumstances: If at any time the constraints of this protocol are detrimental to the patient's health, protocol treatment should be discontinued. In this event submit forms according to the instructions in the MATCH Forms Packet.
- Patient withdraws consent.
- Patient experiences unacceptable toxicity.
- Non-protocol therapies are administered.
- Disease progression

3.7 Duration of Follow-Up

Refer to the MATCH Master Protocol for specifics on the duration of follow-up.

4. Study Parameters

Rev. 12/16
Rev. 3/17
Rev. Add13

4.1 Therapeutic Parameters for GDC-0032 (taselisib) Treatment

NOTE: In addition to the study parameters listed in the MATCH Master Protocol, the below parameters must also be performed for patients receiving GDC-0032 (taselisib) treatment.

NOTE: All assessments required prior to registration to treatment should be done ≤ 4 weeks prior to registration to Steps 1, 3, 5, 7, excluding the radiologic evaluation and electrocardiogram (ECG).

| Test/Assessment | Prior to Registration to Treatment | Treatment | | | End of Treatment | Follow Up ^F |
|--|------------------------------------|---------------------------------|-----------------|----------------|------------------|------------------------|
| | | Every Cycle, prior to treatment | Cycle 1, Day 15 | Every 2 Cycles | | |
| H&P, Weight, Vital signs ^A | X | X ^J | | | | X |
| Performance status | X | X ^J | | | | X |
| CBC w/diff, plts ^B | X | X ^J | | | | X |
| Serum chemistry ^B | X | X ^J | | | | X |
| Fasting blood glucose | X | X ^J | X ^L | | | |
| Radiologic evaluation ^D | X | | | X ^D | | X ^F |
| β-HCG ^C | X | | | | | |
| Toxicity Assessment ^G | | X | | | X | X ^F |
| Pill Count/Diary ^H | | X | | | X | |
| ECG ^K | X | X ^I | | | | |
| Tumor biopsy and blood sample for MATCH Master Protocol ^E | | | | X | X | |

^A. History and physical, including vital signs, pulse oximetry, and weight at the start of each cycle (up to 3 days before start of new cycle).

Rev. 5/16 ^B. Albumin, alkaline phosphatase, total bilirubin, bicarbonate, BUN, calcium, creatinine, phosphorus, potassium, SGOT[AST], SGPT[ALT], sodium, magnesium and serum tumor markers (including LDH, PSA if appropriate). CBC w/diff, platelets and serum chemistries should be performed fasting on cycle 1, day 1 (or up to 7 days prior), and at the start of each subsequent cycle (up to 3 days before start of new cycle). CBC with differential will be performed more frequently in patients with grade 4 neutropenia or thrombocytopenia until resolution to ≤ grade 3. CBC and serum chemistries are only required in follow-up until values return to pre-treatment levels or until progressive disease.

^C. Blood pregnancy test (women of childbearing potential) required prior to beginning treatment.

^D. Disease measurements are repeated every 2 cycles for the first 26 cycles, and every 3 cycles thereafter until PD or start of another MATCH treatment step. The baseline evaluation should be performed as closely as possible to the beginning of treatment and never more than 6 weeks

before registration to treatment step. For multiple myeloma patients, please refer to Section 6.4 of the MATCH Master Protocol for additional information on myeloma response criteria and the required disease assessments. Documentation (radiologic) must be provided for patients removed from study for progressive disease.

- E. Additional blood specimens and/or biopsies are to be submitted from consenting patients per Section 9.3.2 of the MATCH Master Protocol. Submit at the following time points, as applicable:
- Blood specimens are to be submitted at the end of Cycle 2 (prior to start of Cycle 3 treatment). If patient progresses or treatment is discontinued prior to Cycle 3, collect the blood at that time instead. On-treatment kits for blood sample collections will be automatically shipped to sites upon registration to the treatment step.
 - Screening biopsies for additional aMOI assessments after registration to appropriate screening step, if applicable (Step 2 or Step 4).
 - At end of all MATCH study treatments, blood specimens and/or research biopsy after consent and registration to Step 8
- Please refer to Section 4 of the MATCH Master Protocol to determine whether the patient proceeds to the next screening step or to follow-up (with a potential end of treatment biopsy for research purposes on Step 8). Samples are to be submitted as outlined in Section 9 of the MATCH Master Protocol. To order Step 2/4 Screening or Step 8 kits, complete the EAY131 Collection and Shipping Kit Order Form (See Appendix XII of the MATCH Master Protocol) and fax to [contact].
- F. Every 3 months if patient is < 2 years from study entry, and every 6 months for year 3. Toxicity assessments and radiologic evaluations are not required to be done during Follow Up if progression has been previously reported; however if an adverse event occurs post treatment that meets the SAE reporting requirements, it still must be reported via CTEP-AERS, even if progression has occurred.
- G. Site personnel should evaluate for toxicity and discuss treatment compliance with the patient in order to ensure the medication is taken correctly; this evaluation may be conducted by telephone or in person. The Toxicity Assessment is not required prior to Cycle 1, but is required every subsequent cycle.
- H. The pill calendar will be collected at the end of every cycle. The Pill Count/Diary is not required prior to Cycle 1, but is required every subsequent cycle.
- I. As clinically indicated.
- J. For Cycle 1, if the following tests/assessments occurred within 7 days of Day 1, they do not need to be repeated at this timepoint: H&P, Weight, Vital Signs; Performance Status; CBC w/diff, plts; Serum chemistry; Concomitant Medications.
- K. Within 8 weeks of treatment assignment.
- L. Fasting glucose can be drawn day 15 ± 3 days and can be drawn at a local lab.

NOTE: Please provide clear documentation that the glucose test was conducted at a fasting state.

Rev. Add13 **5. Drug Formulation and Procurement**

This information has been prepared by the ECOG-ACRIN Pharmacy and Nursing Committees.

Availability

NO STARTER SUPPLIES MAY BE ORDERED. Subjects must be enrolled and assigned to the treatment subprotocol prior to submitting the clinical drug request to PMB.

Drug Ordering: NCI supplied agents may be requested by eligible participating Investigators (or their authorized designee) at each participating institution. Pharmaceutical Management Branch (PMB) policy requires that drug be shipped directly to the institution where the patient is to be treated. PMB does not permit the transfer of agents between institutions (unless prior approval from PMB is obtained – see general information) The CTEP-assigned protocol number must be used for ordering all CTEP-supplied investigational agents. The eligible participating investigators at each participating institution must be registered with CTEP, DCTD through an annual submission of FDA Form 1572 (Statement of Investigator), NCI Biosketch, Agent Shipment Form, and Financial Disclosure Form (FDF). If there are several participating investigators at one institution, CTEP-supplied investigational agents for the study should be ordered under the name of one lead investigator at that institution.

Submit agent requests through the PMB Online Agent Order Processing (OAOP) application (<https://ctepcore.nci.nih.gov/OAOP>). Access to OAOP requires the establishment of a CTEP Identity and Access Management (IAM) account (<https://ctepcore.nci.nih.gov/iam/>) and the maintenance of an “active” account status, a “current” password, and an active person registration status.

NCI Supplied Agent(s) – General Information

Questions about drug orders, transfers, returns, or accountability should be addressed to the PMB by calling [contact] Monday through Friday between 8:30 AM and 4:30 PM Eastern Time or email [contact] anytime.

Rev. 12/16

Drug Returns: All undispensed drug supplies should be returned to the PMB. When it is necessary to return study drug (e.g., sealed bottles remaining when PMB sends a stock recovery letter), investigators should return the study drug to the PMB using the NCI Return Agent Form available on the NCI home page (<http://ctep.cancer.gov>).

Drug Accountability: The investigator, or a responsible party designated by the investigator, must maintain a careful record of the receipt, disposition, and return of agent received from the PMB using the NCI Investigational Agent Accountability Record Form for Oral Agents available on the NCI home page (<http://ctep.cancer.gov>). Maintain separate NCI Investigational Agent Accountability Records for each agent, strength, formulation and ordering investigator.

Rev. 3/17

Investigator Brochure Availability: The current versions of the IBs for PMB-supplied agents will be accessible to site investigators and research staff through the PMB Online Agent Order Processing (OAOP) application. Access to OAOP requires the establishment of a CTEP Identity and Access Management (IAM) account and the maintenance of an “active” account status, a “current” password, and active person registration status. Questions about IB access may be directed to the PMB IB coordinator at [contact].

Rev. 12/16

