3.1 Dosage and Administration

The dose of GDC-0032 (taselisib) on this study will be 4 mg taken orally once a day (4 mg PO QD) on a 28 day cycle. GDC-0032 (taselisib) is formulated as 2 mg tablets, so patients will take two 2 mg tablets once daily to receive a 4 mg dose. Patients will repeat cycles until progression.

Patients should take the GDC-0032 (taselisib) dose at the same approximate time each day without regard to the timing of administration of food. If a dose is missed (not taken within 6 hours after the scheduled dosing time), the patient should resume dosing with the next scheduled dose. Missed or vomited doses will not be made up.

Guidelines for dosage modification and treatment interruption or discontinuation are provided in Sections [3.4](#) and [3.6](#).

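### Do footnotes D and F set conflicting imaging intervals for a patient who stops drug without progression?

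*Protocol*

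**What the plan says.** The table in Protocol section 4.1 has one row for imaging. It is marked before registration, under Every 2 Cycles (footnote D) and under Follow Up (footnote F). The End of Treatment cell is empty. D also sits on the row label, and F also sits on the Follow Up column heading.

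Footnote D: "Disease measurements are repeated every 2 cycles for the first 26 cycles, and every 3 cycles thereafter until PD". Its stop clause in full is "thereafter until PD or start of another MATCH treatment step". D also holds the timing of the baseline scan and the documentation needed for removal because of progression.

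Footnote F gives the follow-up interval: "Every 3 months if patient is < 2 years from study entry, and every 6 months for year 3". It adds: "Toxicity assessments and radiologic evaluations are not required to be done during Follow Up if progression has been previously reported".

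Three other places bear on the point. Section 3.1 treats cycles as units of dosing: "Patients will repeat cycles until progression". Section 3.6 lets treatment end for reasons other than progression, such as unacceptable toxicity or non-protocol therapy. Section 3.7 defers elsewhere: "Refer to the MATCH Master Protocol for specifics on the duration of follow-up".

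**The concern.** D's stop clause names progression and the start of another MATCH step, but not the end of drug. Its second limb matters only for a patient without progression, because progression already ends D. Such a patient has left taselisib, so the clause can be read as reaching into time off drug. F covers the same patient, since it waives imaging only after reported progression. No sentence says which interval governs.

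Footnote B in the same table seems to sharpen the contrast, because it writes its follow-up limit out: "CBC and serum chemistries are only required in follow-up until values return to pre-treatment levels or until progressive disease". D has no such words. With no scan marked at End of Treatment, the table also does not bridge the two schedules.

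If sites resolved this differently, the recorded date of progression in patients who stop early could depend on the footnote a site followed. Such patients are foreseeable: section 3.4 requires discontinuation for some toxicities, for example Grade 3-4 pneumonitis in Table 3.

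**Working it through.** **Inputs.** A cycle is 28 days and the accrual goal is 70 (Schema). D: every 2 cycles through cycle 26, then every 3. F: every 3 months to 2 years from entry, then every 6 months in year 3. A month is taken as 365.25/12 days. The protocol states no figure of its own to reproduce.

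**Intervals.**
- D: 2 × 28 = 56 days; after cycle 26 (26 × 28 = 728 days, about 2 years), 3 × 28 = 84 days.
- F: 365.25/4 = 91.3 days; in year 3, 365.25/2 = 182.6 days.

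**Wait from progression to the next scheduled scan, first two years.**
- Longest wait equals the interval: 91.3 − 56 = 35.3 days more under F.
- Mean wait is half the interval if progression falls evenly between scans: 45.7 − 28.0 = 17.7 days more under F.

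**Gap from the last on-drug scan to the first off-drug scan.** Let *s* be the stop day, a whole day from 56 to 728, and let the last on-drug scan be on day 56 × floor(*s*/56).
- D continued: 56 days (84 once every-3-cycle imaging begins).
- F counted from the stop: *s* + 91.3 − last scan, which runs from 91.3 to 146.3 days.
- F counted from entry: next multiple of 91.3 after *s*, minus last scan, which runs from 2.5 days (stop on day 728, visit on day 730.5) to about 141.3 days.
- Example, stop on day 100 with the last scan on day 56: next scan on day 112 under D (gap 56), day 182.6 under F from entry (gap 126.6), day 191.3 under F from the stop (gap 135.3).

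**Scan burden.** D gives 365.25/56 = 6.5 scans a year against 4.0 under F in years 1-2. In year 3 it is 365.25/84 = 4.3 against 2.0.

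**Which footnote governs.** Set side by side:
- Column: D marks a Treatment cell; F marks the Follow Up heading and the imaging cell beneath it.
- Unit: D counts cycles, which section 3.1 ties to dosing; F counts calendar months from study entry. Off drug there is no cycle to count.
- Row label: D carries the baseline and documentation rules for the whole row, which is reason enough for it to sit there.
- Footnote B: the blood-test rows have a plain mark under Follow Up, so B must state its own limit. The imaging row already carries F in that cell and needs none.

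These point to D on drug and F off drug. D's stop clause then reads as an outer limit that does not displace the follow-up cell.

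**The case for a change.** The best case for a change is that the clause about another MATCH step has work to do only off drug, that nothing in this document states the handover, and that F does not say from what date its 3 months run after a stop. The Master Protocol cannot be assumed to settle it: section 3.7 defers only the duration of follow-up, and the table applies in addition to the Master Protocol. A short clarification would cost little.

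Much of this stands. The overlap in wording is real and the starting point of F's interval is loose. What is missing is a consequence. The document names no progression-based endpoint, no effect on objective response is argued, and the number of patients who stop without progression is not given. The 35-day and 18-day figures compare two schedules; they do not show bias in a planned estimate.

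The stronger remedy, one calendar-week imaging schedule whatever the drug status, is not a mere reconciliation. It would add scans off drug, change on-drug imaging that now follows cycles, and remove F's six-monthly imaging in year 3. That is a trade-off, and nothing in the text requires it.

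**Conclusion.** No change to the plan follows. D's stop clause is loosely worded and, taken alone, overlaps with F for patients who stop drug without progression. The table layout and the counting in cycles give a workable ordinary reading, and a plan followed on that reading gives sound results.

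For an affected patient in the first two years, the two readings differ by about 35 days in the longest wait for a scan and about 18 days in the mean wait. The mean assumes that progression falls evenly between scans. If every site follows the same footnote, sites do not differ at all. The share of the 70 patients affected cannot be derived from the document.

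The conclusion rests on two assumptions: that sites read the columns as laid out, and that nothing in the Master Protocol, which was not available, contradicts that reading. A line saying whether D ends with drug, and from what date F then runs, would be tidier, but it would only write down the handover the table already implies.

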5.1 GDC-0032 (NSC #778795)

5.1.1 Other Names

Taselisib, RG7606

5.1.2 Classification

PI3K inhibitor

5.1.3 Mode of Action

Inhibition of PI3K pathway components such as Akt, PRAS40, and S6, resulting in G1 arrest and apoptosis.

5.1.4 Storage and Stability

Storage: GDC-0032 tablets should not be stored above 25°C.

Stability: Shelf-life surveillance of the intact bottles is ongoing.

If a storage temperature excursion is identified, promptly return GDC-0032 (taselisib) to ambient temperature and quarantine the supplies. Provide a detailed report of the excursion (including documentation of temperature monitoring and duration of the excursion) to [contact] for determination of suitability.

5.1.5 Dose Specifics

Two 2-mg GDC-0032 tablets will be administered orally once a day on a continuous daily dosing schedule.

5.1.6 How Supplied

Genentech supplies and PMB, CTEP, DCTD distributes GDC-0032 as white, film-coated, immediate-release 2 mg tablets. The tablet formulation consists of GDC-0032 active, lactose monohydrate, microcrystalline cellulose, croscarmellose sodium, magnesium stearate, and Opadry 2 white film-coating. The film-coating consists of polyvinyl alcohol-part hydrolyzed, titanium dioxide, polyethylene glycol 3350, and talc. Each bottle contains 30 film-coated tablets.

5.1.7 Route of Administration

GDC-0032 is taken orally, and may be taken with or without food.

5.1.8 Method of Administration

GDC-0032 may be taken with or without food.

5.1.9 Incompatibilities

GDC-0032 is metabolized via CYP3A4/5. GDC-0032 should not be administered with strong CYP3A4/5 inhibitors/inducers and administered with caution when combined with moderate CYP3A4/5 inhibitors/inducers. No drug-drug interactions were observed in cancer patients with the following CYP3A4 substrates: midazolam, letrozole, or fulvestrant. Grapefruit and grapefruit juice should be avoided due to the risk of increased GDC-0032 exposure.

Avoid grapefruit/ grapefruit juice and Seville oranges while participating in this trial.

In vitro studies showed that taselisib was a substrate of P-glycoprotein (P-gp) and breast cancer resistance protein (BCRP). In vitro testing also found GDC-0032 to be an inhibitor of OATP1B1, OATP1B3, OCT1, OCT2 and OAT3. GDC-0032 was also found to not be a potent inhibitor of CYP isoforms 1A2, 2B6, 2C8, 2C9, 2C19, 2D6 or 3A4/5 or transporters P-gp, BCRP or OAT1.

5.1.10 Side Effects

See Section [3.3](#) for side effects.

5.1.11 Nursing/Patient Implications

- Hyperglycemia (Grades 1-4) was reported in approximately 32% of the patients who received GDC-0032 as a single agent. Patients with diabetes mellitus requiring insulin therapy should be excluded from studies of GDC-0032. Glucose levels should be carefully monitored at baseline and during study per individual protocol guidelines. Patients should be instructed to report symptoms associated with hyperglycemia, such as thirst, frequent urination, and blurred vision. Anti-hyperglycemic agents should be used to control severe hyperglycemia per institutional standard of care.
- Non-infectious pneumonitis has been observed in patients treated with GDC-0032 QD, with onset at approximately Day 66-167 days post dosing. Patients who require any daily supplemental oxygen should not be recruited for the study.
- Reproductive Risks:
 - Women of child bearing potential and male patients should continue contraceptive measures for 4 months after the last dose of GDC-0032.

6. Translational Studies

Please refer to the MATCH Master Protocol for information on the Translational Studies.

7. References

1. Cantley LC. The phosphoinositide 3-kinase pathway. *Science*. 2002;296(5573):1655-1657.

Appendix I

Patient Pill Calendar

Storage: Store at Room Temperature

Pill Calendar Directions

1. Take your scheduled dose of two 2-mg tablets, which will be administered orally once a day, at approximately the same time each day.
2. If you forget to take your dose at the scheduled time, you may take it within 6 hours after the usual time. If the dose is not taken within 6 hours of the usual time, the missed tablets will not be taken later. Instead, resume your dose the next day.
3. Please bring the empty bottle or any leftover tablets and your pill calendar to your next clinic visit.
4. Tablets will be taken once a day, at approximately the same time each day, with a full glass of water, with or without food.
5. Swallow tablets whole, do not crush or chew tablets.

Patient Pill Calendar

This is a calendar on which you are to record the time and number of tablets you take each day. You should take your scheduled dose of each tablet. **Note the times and the number of tablets that you take each day.** If you develop any side effects, please record them and anything you would like to tell the doctor in the space provided. Bring any unused tablets and your completed pill calendar to your doctor's visits.

GDC-0032 (taselisib)

| DAY | Date | | | Time tablets taken | Number of tablets taken | Use the space below to make notes about things you would like to tell the doctor (including unusual symptoms you experience, other medicine you have taken and anything else you think would be of interest.) |
|-----|-------|-----|------|--------------------|-------------------------|---|
| | Month | Day | Year | | | |
| 1 | | | | | | |
| 2 | | | | | | |
| 3 | | | | | | |
| 4 | | | | | | |
| 5 | | | | | | |
| 6 | | | | | | |
| 7 | | | | | | |
| 8 | | | | | | |
| 9 | | | | | | |
| 10 | | | | | | |
| 11 | | | | | | |
| 12 | | | | | | |
| 13 | | | | | | |
| 14 | | | | | | |
| 15 | | | | | | |
| 16 | | | | | | |
| 17 | | | | | | |
| 18 | | | | | | |
| 19 | | | | | | |
| 20 | | | | | | |
| 21 | | | | | | |
| 22 | | | | | | |
| 23 | | | | | | |
| 24 | | | | | | |
| 25 | | | | | | |
| 26 | | | | | | |
| 27 | | | | | | |
| 28 | | | | | | |

Patient Signature: _____ Date: _____

**Molecular Analysis for Therapy Choice (MATCH)
MATCH Treatment Subprotocol I: GDC-0032 (taselisib)**

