3.4 Dose Modifications

All toxicity grades below are described using the NCI Common Terminology Criteria for Adverse Events (CTCAE) version 4.0.

All appropriate treatment areas should have access to a copy of the CTCAE version 4.0. A copy of the CTCAE version 4.0 can be downloaded from the CTEP website (<http://ctep.cancer.gov>).

The side effects observed with GDC-0032 (taselisib) are consistent with those observed with other PI3K inhibitors. Selected toxicities of interest for GDC-0032 (taselisib) include gastrointestinal toxicities, pneumonitis, rash, stomatitis, and hyperglycemia and these are described in detail below. Certain adverse events (e.g., rash, colitis, and pneumonitis) may also occur within 4 weeks of holding or stopping GDC-0032 (taselisib).

The GDC-0032 (taselisib) dose reduction instructions provided in **Table 1** are intended to serve as recommended guidelines to allow ongoing treatment for patients experiencing clinical benefit without signs or symptoms of progression while monitoring patient safety. The investigator may temporarily suspend GDC-0032 (taselisib) dosing for up to 28 days from the last scheduled dose due to a GDC-0032 (taselisib)-related toxicity or an unanticipated medical event not associated with study treatment toxicity or with disease progression. Depending on the nature and the severity of the GDC-0032 (taselisib)-related toxicity, the investigator may resume GDC-0032 (taselisib) dosing in the patient at the same dose or at one dose level lower (as detailed in Tables 2–6).

Table 1 Overall Dose Modification Guideline for GDC-0032 (taselisib)-Related Adverse Events

| | GDC-0032 (taselisib) |
|------------------|----------------------------|
| Starting dose | 4 mg daily |
| First reduction | 2 mg daily |
| Second reduction | 2 mg every other day (QOD) |

No dose reduction is allowed for patients treated at a dose of GDC-0032 (taselisib) of 2mg QOD – if there is an indication for further dose reduction, the patient must permanently discontinue GDC-0032 (taselisib). Dose re-escalation is not allowed after a dose reduction.

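### The patient pill calendar fixes the starting dose in print, so it is wrong for any patient whose dose has been reduced under Table 1

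*Protocol*

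**What the plan says.** Section 3.1 sets the starting regimen: "patients will take two 2 mg tablets once daily to receive a 4 mg dose". Section 5.1.5 repeats it without mentioning reductions.

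Table 1 in Section 3.4 gives two lower levels, 2 mg daily and then 2 mg on alternate days. Below the table the protocol adds: "Dose re-escalation is not allowed after a dose reduction". Section 5.1.6 describes a single tablet strength, 2 mg.

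The directions in Appendix I, which the patient takes home, assume the starting dose throughout:

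- Direction 1: "Take your scheduled dose of two 2-mg tablets, which will be administered orally once a day".
- Direction 4: "Tablets will be taken once a day, at approximately the same time each day".
- Direction 2, on a dose missed by more than 6 hours: "Instead, resume your dose the next day". Section 3.1 words the same rule differently: "the patient should resume dosing with the next scheduled dose".

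The grid has columns for day, date, time, number of tablets taken and notes. None states what was prescribed. The calendar is collected at the end of each cycle (Section 4.1, footnote H), so it remains in use after a reduction.

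**The concern.** The printed directions are correct only while the patient is at 4 mg daily. Once the dose is reduced, the form contradicts the prescription, and the people affected are those who have already had toxicity on the higher dose. A patient who followed the print would be back at 4 mg daily, the exposure that the rule against re-escalation is meant to prevent.

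Reduction is a planned path in this protocol. Restarting one level lower is specified for:

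- Grade 2 pneumonitis that recovers (Table 3);
- several forms of Grade 2 diarrhea, Grade 2 colitis, and a first Grade 3 episode of either (Table 5);
- recurrent Grade 2 and Grade 3 stomatitis (Table 6).

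It is also one of the options for severe rash (Table 4) and for severe hyperglycemia (Table 2). Section 3.4 puts the average onset of severe steroid-responsive diarrhea at 4 to 6 months, so such a patient would already have used several calendars that state two tablets.

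There is a smaller data cost. The form records intake but not the prescribed dose, so the calendar alone cannot show whether a reduced patient complied.

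**Working it through.** The protocol gives no figure to reproduce here. The check sets the printed directions against Table 1 and counts tablets.

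**Inputs**

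- Cycle length: 28 days (Section 3.1).
- Tablet strength: 2 mg (Sections 3.1 and 5.1.6).
- Printed directions: 2 tablets on each of 28 days (Appendix I, directions 1 and 4).
- First reduction: 2 mg daily, which is 1 tablet on each of 28 days (Table 1).
- Second reduction: 2 mg on alternate days, which is 1 tablet on 28 / 2 = 14 days (Table 1).

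**Formula**

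Tablets per cycle = tablets per dose × dosing days. Milligrams per cycle = tablets × 2.

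**Results**

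| Patient's level | Intended tablets | Intended mg | Printed tablets | Printed mg | Excess tablets | Excess mg | Printed / intended |
|---|---|---|---|---|---|---|---|
| 4 mg daily | 2 × 28 = 56 | 112 | 56 | 112 | 0 | 0 | 1.0 |
| 2 mg daily | 1 × 28 = 28 | 56 | 56 | 112 | 28 | 56 | 112 / 56 = 2.0 |
| 2 mg alternate days | 1 × 14 = 14 | 28 | 56 | 112 | 42 | 84 | 112 / 28 = 4.0 |

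**Which directions fail, and where**

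- Direction 1 (count and frequency): the count is wrong at both reduced levels, and the frequency is also wrong at the second.
- Direction 4 (frequency): wrong at the second reduction.
- Direction 2 (missed dose): differs from Section 3.1 at the second reduction. For an alternate-day patient it only moves the missed dose and adds no drug.

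**Whether other wording on the form repairs this**

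The calendar also tells patients, in general terms, to take their scheduled dose. Direction 1 has already defined that dose as two tablets once a day, so the general sentence points back to the wrong figure.

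**The case against.** The best defense is that the calendar is a diary and not a dosing order. The dose level is set by Section 3.4 and the investigator, and a reduced patient can write 1, or nothing on off days, in the column for tablets taken. Most reductions also follow a deliberate hold and restart. Restarting after severe rash requires discussion with the overall principal investigator, and restarting after asymptomatic Grade 3 hyperglycemia requires it with the study principal investigator. To follow the print, a patient would have to ignore an instruction just received after a drug interruption.

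There are further checks. Footnote G in Section 4.1 has site staff "discuss treatment compliance with the patient in order to ensure the medication is taken correctly". Pill counts are made and calendars collected every cycle after the first, and leftover tablets are brought back. The 2-fold and 4-fold figures therefore assume a full cycle without correction. Strictly, a patient who misreads a form makes a dosing error, which is not a re-escalation decision under Section 3.4. Finally, the MATCH Master Protocol and the Appendix III handout were not available for this review and may say something about changed doses.

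Much of this stands. It lowers the chance of an error, shortens its likely duration, and makes the multiples upper limits. It does not make the form right. Pill counts find an error after the tablets have been taken, and verbal instructions compete with a printed direction that the patient consults at home. Whatever the unseen materials say, this page would still state a superseded dose.

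**Conclusion.** The concern holds. Appendix I states a dose that is wrong for every patient at either reduced level of Table 1. Followed for a full 28-day cycle, it gives 2 times the intended amount at 2 mg daily (28 extra tablets, 56 mg) and 4 times on average at 2 mg on alternate days (42 extra tablets, 84 mg).

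Those figures assume complete adherence to the print and no correction within the cycle. The protocol gives no basis for how many patients will be reduced or how many would follow the form over the investigator, so no patient count is claimed. Confidence is high that the printed text conflicts with Table 1. The remaining risk after verbal instruction cannot be quantified from this document.

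This is a patient-instruction and dosing-safety matter that should be fixed. It affects no endpoint, sample size or analysis. The missed-dose wording in direction 2 is minor.

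**What to change.** In Appendix I:

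1. Replace the fixed count and frequency in directions 1 and 4 with two fields, the number of 2 mg tablets per dose and a choice of every day or every other day. The site completes them each cycle from the patient's current Table 1 level.
2. Require a new calendar whenever the dose is reduced, including within a cycle, and retrieval of the old one.
3. Reword direction 2 so that a patient who misses a dose resumes with the next scheduled one, in line with Section 3.1.

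A pointer from Section 5.1.5 to Table 1 would help but is optional.

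The cost is a wording change to three directions in one appendix and redistribution of the form. Dose levels, visit schedule, design and analysis stay as they are.
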